LDi	longest transverse diameter of a lesion
LPD	longest perpendicular dimension

Protocol: LAM-002A-NHL-CLN01

Version 9, 18 Feb 2020

Table 1: Abbreviations and Specialist Terms (Continued)

Abbreviation or Specialist Term	Explanation
MCL	mantle cell lymphoma
MedDRA	medical dictionary for regulatory activities
mg/kg/day	milligram/kilogram/day
mL	milliliter
MRD	minimal residual disease
MRI	magnetic resonance imaging
MTD	maximum tolerated dose
MZL	marginal zone lymphoma
NCI CTCAE	National Cancer Institute common terminology criteria for adverse events
NHL	Non-Hodgkin's lymphoma
nM	nanomolar
NOEL	no observed effect level
PBMC	peripheral blood mononuclear cells
PD	progressive disease
PDs	pharmacodynamics
PE	physical examination
PET	positron emission tomography
PFS	progression-free survival
PI	phosphatidyl inositol
PIKfyve	phosphatidylinositol-3-phosphate- 5 kinase
PK	pharmacokinetics
PPD	cross product of the longest transverse diameter of a lesion and perpendicular diameter
PR	partial remission
PSA	prostate specific antigen
QD	once daily ("quaque die")
QRS	combination of 3 of the graphical deflections seen on a typical electrocardiogram (ECG)
QT	time of start of Q wave until end of T wave in the heart's electrical cycle
QTc	corrected QT interval
QTcF	Fridericia correction formula
R	accumulation ratio

Protocol: LAM-002A-NHL-CLN01

Version 9, 18 Feb 2020

Table 1: Abbreviations and Specialist Terms (Continued)

R-CHOP	rituximab, cyclophosphamide, doxorubicin, vincristine, and prednisone
RBC	red blood cell
RNA	ribonucleic acid
RNAi	RNA interference
RP2D	recommended Phase 2 dose
SAE	serious adverse event
SAP	statistical analysis plan
SAS	statistical analysis system
SD	stable disease
SDi	shortest axis perpendicular to the LDi
SLL	small lymphocytic lymphoma
SOP	standard operating procedure
SPD	sum of the product of the perpendicular diameters for multiple lesions
t _{1/2}	terminal elimination half-life
ТВ	tuberculosis
T-CLL	T-cell chronic lymphocytic leukemia
Th1	T-helper cell phenotype
TID	thrice per day
TLS	tumor lysis syndrome
t _{max}	time to maximum concentration
ULN	upper limit of normal
WBC	white blood cell
WCBP	women of child bearing potential
WHO	World Health Organization
WHODD	World Health Organization drug dictionary

Version 9, 18 Feb 2020

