4.1.4. Pharmacokinetics, Clinical Efficacy and Safety

4.1.4.1. Pharmacokinetics

In humans, apilimod is orally bioavailable, rapidly absorbed, and extensively metabolized. Pharmacokinetic studies revealed generally dose-dependent increases in both C_{max} and AUC. t_{max} following oral administration was 1 hour in the absence of food and 2 to 3 hours when taken with food; in normal healthy volunteers and subjects with psoriasis, t_{max} ranged from 2 to 4 hours. Approximately 90% or more of the absorbed drug was cleared from circulation within 8 to 10 hours following administration, after which any remaining drug was eliminated with a terminal half-life of 5 to 10 hours following administration on the first day, increasing to 12 to 21 hours on Day 14. These findings suggest that either daily (QD) or BID dosing regimens may be appropriate. A small food effect was observed but is not deemed to be clinically significant.

The 2 dosage forms (apilimod dimesylate and apilimod formulations) used to date in clinical trials are bioequivalent. The 50-mg dose of apilimod dimesylate provides the same amount of active ingredient as the previously used 35-mg capsule of apilimod. Similarly, a 100-mg dose of apilimod dimesylate is equivalent to 70 mg apilimod. Future studies will utilize apilimod dimesylate capsules (LAM-002A).

Version 9, 18 Feb 2020

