5.5. Secondary Endpoints

- Standard PK parameters including but not limited to AUC, t_{1/2} and C_{max}
- The type and frequency of AEs, serious adverse events (SAEs) using National Cancer Institute (NCI) CTCAE v4.0 (Common Toxicity Criteria for Adverse Events, version 4.0) as well as changes in clinical laboratory values, electrocardiogram (ECG) parameters and vital sign measurements
- Response as assessed by the investigator according to modified Lugano Response Criteria for NHL (Cheson 2014) and revised guidelines for the diagnosis and treatment of CLL (Hallek 2008, Cheson 2012)

Version 9, 18 Feb 2020

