6.8.2.3. LAM-002A Self-Administration

Except for the days where treatment is administered in the clinic, LAM-002A will be self-administered orally, BID or TID of each 28-day cycle until disease progression or other discontinuation criteria are met. When taking the drug at home, subjects should be advised to take LAM-002A with \geq 4 oz. (\sim 160 mL) of water at the same times each day. Subjects on a BID schedule will be advised to take the doses at \sim 12 hours apart (e.g., 8:00 AM and 8:00 PM) (+/-1-hour window). Subjects on a TID schedule will be advised to take the doses at intervals of \sim 6 to 8 hours. When self-administering LAM-002A at home, subjects may take the drug in the fed or fasted state. On PK days, subjects should come to clinic fasted (a minimum fasting state of 6 to 8 hours) and take the dose at the site under supervision. All subjects will be required to complete a dosing diary, which must be returned to the site for review at each site visit.

For those subjects taking LAM-002A with continuous administration, the drug should be taken according the prescribed BID or TID schedule without interruption unless toxicity or intercurrent illness requires a modification to the dosing regimen (see Section 6.8.2.5).

For those subjects taking LAM-002A with intermittent administration, the drug should be taken in repeated 7-day sequences comprising BID self-administration for 3 days (6 doses) followed by 4 days without dosing. If the cadence of the on-off periods is interrupted due to toxicity, intercurrent illness, or other reasons, the medical monitor should be consulted regarding the timing of therapy resumption and dose modification (see Section 6.8.2.5).

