- M Subjects with CLL/SLL must provide either a fresh blood sample containing circulating tumor cells or a bone marrow aspirate sample pretreatment. Tissue will be submitted for evaluation of the percentage of tumor cells and analysis of genetic alterations and/or gene expression that may predict anticancer activity and/or pharmacodynamic activity. In addition, for subjects with CLL/SLL, the sponsor may arrange for a portion of the sample to be evaluated at a sponsor-specified laboratory for known prognostic markers (e.g., quantitative immunoglobulins, FISH panel [chromosome 11q deletion, 13q deletion, 17p deletion and 12 trisomy], DNA mutational analysis for p53, IgHV [including IgHV3-21], and other genes of interest in CLL [e.g., Notch]; flow cytometry [for CD5, CD10, CD11c, CD19, CD20, CD23, CD38, CD45, kappa and lambda light chains and ZAP-70], and/or β2-microglobulin). The baseline bone marrow aspiration procedure (if required) should be performed after the study candidate has undergone the baseline radiology examination and is otherwise considered eligible for study participation. All subjects with CLL/SLL must have baseline imaging (with CT scans [preferred] or MRI scans).
- N Blood sampling for determination of the plasma concentrations and activity of LAM-002A and metabolites will be performed on C1D1 and C1D8 as follows: pre-dose, 30 minutes, 1, 2, 4, 6, 8 hours post-first dose of the day. Sampling on C1D15 will be pre-dose only. Subjects are required to come to the study site in a fasting state prior to the collection of certain PK samples.

Protocol: LAM-002A-NHL-CLN01

Version 9, 18 Feb 2020

- O Bone marrow aspirates/biopsies performed within 2 months prior to first dose may be used for clinical baseline assessments. For subjects with NHL, baseline bone marrow biopsies/aspirates may be omitted if not deemed essential for response assessment or patient management and there is another source of tumor tissue for pretreatment evaluation of gene expression and prognosis. For subjects with CLL/SLL, a baseline bone marrow aspirate is required unless the presence of sufficient circulating cells in the peripheral blood (e.g., absolute lymphocyte count [ALC] $\geq 10 \times 10^9$ /L) permits assessment of baseline parameters as described in Footnote m, above.
- P If necessary per applicable response criteria, a repeat bone marrow biopsy or aspirate will be required for subjects who have a CR by imaging and physical examination.

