12. PHARMOCOKINETIC ASSESSMENTS

Plasma concentration levels of apilimod and the active metabolites will be measured in the doseescalation and dose-expansion stages at each of the specified time points; Table 8: Schedule of Assessments (LAM-002A Continuous Monotherapy Administration), Table 9: Schedule of Assessments (LAM-002A Intermittent Monotherapy Administration), Table 10: Assessments (LAM-002A/Rituximab Combination Therapy), and Table 11: Schedule of Assessments (LAM-002A/Atezolizumab Combination Therapy) in Section 8.7. The analytical laboratory will measure plasma concentrations of apilimod using a validated analytic method. PK parameters will be estimated using standard non-compartmental methods will include: C_{max}, t_{max}, AUC_{0-t}, AUC₇; t_{1/2}, trough concentrations on Days 8 and 15, and a comparison of AUC_{0-t} from Days 1 and 8 or Days 1 and Day 10 (as appropriate); additional parameters may be determined based on the available data. Accumulation will be assessed by calculating the accumulation ratios I for C_{max} and AUC when comparing Day 8 to Day 1 for all continuous LAM-002A regimens (whether given as monotherapy or in combination) or when comparing Day 10 to Day 1 for the intermittent LAM-002A regimen. Dose proportionality for C_{max} and AUC_{0-t} will be assessed by applying an appropriate power model to the data. Descriptive statistics of PK parameters will include minimum, maximum, mean, standard deviation, percent coefficient of variation (%CV), and range.

Pharmacokinetic samples will be collected for determination of plasma apilimod and active metabolite concentrations at the time points indicated in Table 13. All subjects must participate in PK assessments. Fasting status must be recorded at the time of each PK blood draw.

Protocol: LAM-002A-NHL-CLN01

Version 9, 18 Feb 2020

Table 13: Pharmacokinetic Sampling Time Points

Sample	Study Day	PK Sampling Time Points ^a
1 ^b	1	Pre-dose (within 30 min prior to dose of LAM-002A)
2	1	0.5 hour (± 10 min) after dosing with LAM-002A
3	1	1 hour (± 10 min) after dosing with LAM-002A
4	1	2 hours (± 10 min) after dosing with LAM-002A
5	1	4 hours (± 10 min) after dosing with LAM-002A
6	1	6 hours (± 10 min) after dosing with LAM-002A
7	1	8 hours (± 10 min) after dosing with LAM-002A
8 ^b	8 or 10 ^c	Pre-dose (within 30 min prior to dose of LAM-002A)
9	8 or 10 ^c	0.5 hour (± 10 min) after dosing with LAM-002A
10	8 or 10 ^c	1 hour (± 10 min) after dosing with LAM-002A

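### Post-dose sampling to 8 hours cannot support t1/2 as a terminal half-life, and the Day 8 and Day 15 troughs on the intermittent schedule are washout values

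*Combined protocol and SAP*

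**What the plan says.** Section 5.5 lists "Standard PK parameters including but not limited to AUC" as a secondary endpoint and goes on to name t1/2 and Cmax. Table 1 (Section 3) expands t1/2 as "terminal elimination half-life". Section 12 states that "PK parameters will be estimated using standard non-compartmental methods" and includes t1/2 in the list.

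For continuous monotherapy, Table 8 footnote N has blood sampling "performed on C1D1 and C1D8 as follows: pre-dose, 30 minutes, 1, 2, 4, 6, 8 hours post-first dose of the day". Tables 10 and 11 repeat this for the combinations. Table 9 uses the same times on Days 1 and 10 for the intermittent regimen. In Table 13 the last post-dose sample is at 8 h throughout.

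Section 4.1.4.1 summarises earlier human data: about 90% or more of absorbed drug had cleared by 8 to 10 h, "after which any remaining drug was eliminated with a terminal half-life of 5 to 10 hours following administration on the first day", rising to 12-21 h on Day 14.

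Section 12 also lists "trough concentrations on Days 8 and 15" without separating regimens. Section 6.8.2.3 describes intermittent dosing as "repeated 7-day sequences comprising BID self-administration for 3 days (6 doses) followed by 4 days without dosing". On that schedule, Table 9 takes only a predose sample on Days 8 and 15.

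**The concern.** Two planned PK outputs carry names that the sampling does not support.

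First, a terminal half-life needs samples in the terminal phase. By the plan's own account that phase begins at about the time sampling ends. A non-compartmental routine will still return a number from the last few points. Reported under the Table 1 definition, that number would appear to contradict Section 4.1.4.1.

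Second, a trough is normally the concentration at the end of a dosing interval during treatment. On the intermittent schedule, Days 8 and 15 are the first dosing days after four days off. Shown beside continuous-regimen troughs, these values would not be like for like.

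PK is the first-listed secondary objective, and Sections 6.6 and 6.1.1 make PK data one input to dose and schedule decisions, so the labels should be right.

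**Working it through.** **Inputs.** Last post-dose sample 8 h (Tables 8-11 and 13). About 90% or more cleared by 8-10 h; terminal half-life 5-10 h on the first day and 12-21 h on Day 14; tmax 1-4 h across the conditions described (all Section 4.1.4.1). Intermittent dosing 3 days on, 4 off, with example dose times of 8 AM and 8 PM (Section 6.8.2.3).

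**The plan's own figures.** The stated half-lives are empirical and come without source data, so they cannot be re-derived. The schedule arithmetic does reproduce: 4 weeks × 3 days × 2 doses = 24 doses per cycle, and 75% of 24 = 18, matching the 18/24 evaluability rule in Section 6.6.

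**Half-life: coverage of the terminal phase.** No post-dose sample falls after 8 h, so at most one point touches the early edge of the 8-10 h onset. The 4-8 h segment covers:
- Day 1: 4/10 to 4/5 = 0.4 to 0.8 of a terminal half-life.
- Day 14 values: 4/21 to 4/12 = 0.19 to 0.33 of a terminal half-life.

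**Half-life: the phase that is sampled.** For a single-exponential 90% fall over time T, t1/2 = T × ln 2 / ln 10 = 0.301 × T.
- From time zero to 8 or 10 h: 2.4 or 3.0 h.
- From the peak (1-4 h) to 8-10 h: shortest 0.301 × (8 − 4) = 1.2 h; longest 0.301 × (10 − 1) = 2.7 h.

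**Half-life: a two-phase curve.** Assume C(t) = (1 − B)·exp(−at) + B·exp(−bt), choose B so that 10% remains at 8 or 10 h, and fit a log-linear line to the 4, 6 and 8 h points. The two-phase shape, the early half-life of 1-2.5 h, reading 90% cleared as a concentration falling to exactly 10%, and ignoring absorption are all assumptions made here, not in the documents.

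Example: early half-life 1.5 h, true terminal half-life 10 h, 10% left at 8 h. Then B = 0.137, and C(4), C(6), C(8) = 0.240, 0.144, 0.100. The fitted half-life is 3.17 h, or 32% of the true value.

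| True terminal t1/2 | Fitted 4-8 h t1/2 | Share of true value |
|---|---|---|
| 5-10 h | 2.6-5.2 h | 26-80% |
| 12-21 h | 2.6-5.9 h | 13-45% |

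A second parameterisation starts the decline at tmax (1-4 h), sets the 90% fall to end at 8-10 h, and uses a terminal fraction of 5-12%. It gives 1.2-3.9 h for true values of 5-21 h. Every case tried falls below the true value; the size of the shortfall depends on the model.

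**Intermittent troughs.** From 8 PM on Day 3 to 8 AM on Day 8 is 5 × 24 − 12 = 108 h. The same gap separates Day 10 from Day 15. The fraction remaining is 0.5^(108 / t1/2):
- t1/2 = 12 h: 9.0 half-lives, 0.2%.
- t1/2 = 21 h: 5.1 half-lives, 2.8%.
- t1/2 = 5-10 h: 21.6 to 10.8 half-lives, 0.06% or less.

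The Day 10 predose sample follows the Day 9 evening dose by about 12 h, so it is an on-treatment trough. Table 13 already collects it, and Section 12 already uses Day 10 for accumulation, but not for trough.

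**The case against.** The case against making much of this has real force.

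- t1/2 is one item in an open-ended list, and the word terminal comes only from the abbreviation table. Section 14.2 defers detailed methods to a SAP, and only part of the combined document is available. Rules for accepting or omitting t1/2 may exist elsewhere. This limits what can be said about what will be reported, but it does not add samples after 8 h.
- No decision rule uses t1/2. Section 12 assesses dose proportionality and accumulation on Cmax and AUC, PK may inform the RP2D only as supporting rationale, and Section 6.1.2 already sets the expansion starting regimen. This stands, and it limits the consequence.
- For TID dosing, sampling to 8 h covers the 6-8 h interval. This stands for exposure over the interval, but not for terminal half-life.
- The trough problem is one of labelling in a single regimen, and the Day 10 data are already planned. This stands, and it is why the repair is cheap.

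A reader might infer that the fit will return about 2 h whatever the truth, and so carries no information. That narrow result appears only when the curve is pinned to one particular shape; other reasonable settings give 1.2-5.9 h. A reader might also infer that low Day 8 values would be taken to mean no exposure between doses on treatment days. The full Day 10 profile makes that unlikely.

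**Conclusion.** The point holds as a mismatch between named outputs and planned samples. The half-life that can be estimated is an apparent early-phase value, biased low relative to the terminal values in Section 4.1.4.1. The direction rests on the plan's own description of when the terminal phase starts. The size, roughly 1-6 h against 5-21 h, rests on assumed two-phase curves and is only indicative. The onset time itself comes from earlier studies outside lymphoma.

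The intermittent Day 8 and Day 15 predose samples are washout concentrations. This follows from the calendar; only the residual of 0.2-2.8% depends on the half-life assumed (12-21 h).

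The documents do not support extending the criticism to PK as a whole, or saying that a dose or schedule decision would be wrong because of it.

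**What to change.** Amend Sections 5.5 and 12, and the corresponding PK analysis text:

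1. Report t1/2 as apparent half-life over a stated post-peak window, for example 4-8 h, and do not present or interpret it as terminal elimination half-life. A window opening at 2 h is less safe, because Section 4.1.4.1 gives tmax values up to 4 h.
2. For intermittent cohorts, define the on-treatment trough as the Day 10 predose sample, and label the Day 8 and Day 15 predose samples as end-of-off-period (washout) concentrations. Leave the continuous-regimen troughs as they are.
3. Optionally, for continuous BID, use the Day 8 predose value as an approximate 12 h steady-state concentration for AUC0-12, labelled as such. It follows a home evening dose with looser control of food and timing.

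Two apparent rescues should be avoided. An 8-12 h slope would join two points from different doses. An effective half-life from the Day 8/Day 1 AUC ratio needs a Day 1 AUC0-12 that is not sampled, and PK that does not change over time, whereas Section 4.1.4.1 reports a change.

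The cost is wording only, with no new sample and no change to dosing. The downside is that a terminal half-life is no longer claimed.

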A 3 + 3 design will be utilized to define an MTD. For cohorts consisting of 3 subjects, dose escalation to the next higher dose may proceed if no DLT is observed within the first cycle of the 3 evaluable subjects accrued to a cohort (See Section 6.1.1). If 1 of 3 subjects in the cohort experiences a DLT, up to a total of 6 evaluable subjects will be enrolled. If 2 or more of the 3-6 evaluable subjects in a cohort experience a DLT, dose escalation will cease, and additional subjects will be treated at a lower dose level or with another schedule. If de-escalation to the previous dose cohort is undertaken, this cohort may be expanded to \geq 6 subjects. Additional subjects (up to 12 total per cohort) may be evaluated to refine the estimation of the MTD and RP2D at the planned dose levels or at an intermediate dose level between the highest previously tolerated total dose and the next planned total daily dose. The MTD is defined as the highest dose at which \leq 33% of subjects experience a DLT in the total dose cohort.

Dose escalation decisions will be evaluated in a DLT-evaluable population. The DLT-evaluable population will include subjects who complete Cycle 1 dosing or who are withdrawn from study due to a DLT in Cycle 1. A subject will be deemed non-evaluable for determining DLTs and will not be counted toward the total cohort size if the subject did not experience a DLT, did not

receive at least 75% (42/56 BID schedule; 63/84 TID schedule, 18/24 intermittent schedule) of the planned first-cycle doses or discontinued from the study prior to completing necessary safety evaluations through the first 28 days of study treatment. These subjects may be replaced unless accrual to the cohort has stopped due to DLT.

Following the above guidelines, the participating investigators and sponsor will review available data including toxicity, PK and anti-tumor activity data to reach consensus on dose levels and determination of the MTD. This group will review available safety data for each cohort and will determine whether the MTD has been reached and decide upon further subject enrollment. Any detected cumulative toxicity may require later dose reductions or other action as appropriate, and may be evaluated in determining the RP2D and schedule.

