6.8.2.6.2. Antiemetics for Subjects Taking LAM-002A by Intermittent Administration

Because LAM-002A induces dose-dependent nausea and vomiting, subjects who are taking LAM-002A by intermittent administration are required to receive antiemetic supportive care.

Version 9, 18 Feb 2020

The following prophylaxis regimen should be started ≥30 minutes before initiation of each LAM-002A 3-day treatment sequence:

- Dexamethasone 12 mg PO on Day 1 and then 8 mg PO on Day 2 and Day 3
- Granisetron 2 mg PO on Day 1 and then 1 mg PO BID on Days 2 and 3
- Olanzapine, 10 mg PO on Day 1 and then 10 mg PO on Days 2 and 3

The study subject must be sent home from the clinic with sufficient dexamethasone, granisetron, and olanzapine to ensure that the supportive care medications are readily available to the subject for each of the four 3-day courses of LAM-002A therapy during each 28-day cycle.

Doses of dexamethasone and olanzapine may be adjusted to tolerance. Other antiemetic drugs (eg, neurokinin 1 receptor antagonists, dopamine antagonists, or benzodiazepines) may be considered in consultation with the medical monitor.

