8.2.5. Vital Signs

Vital signs including temperature (°C), blood pressure, pulse, and respiration rate will be measured at each indicated visit including screening, prior to the start of each cycle, prior to each PK time point, at the End of Treatment, and more often if clinically indicated.

Version 9, 18 Feb 2020

8.3. Screening/Baseline, Day 1, 8, 10, 15 (Cycles 1 and 2 Only) and Prior to Each Subsequent Cycle and End of Treatment

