8.3.1. Clinical Laboratory Tests

Clinical laboratory tests during the first 2 cycles will be performed by the investigative site's local laboratory. Samples will be collected from subjects at scheduled study visits before the administration of study drug unless otherwise noted, and more frequently if clinically indicated. Clinical laboratory tests may be performed up to 72 hours prior to the scheduled visits (see Section 8.7 for Schedules of Assessments). Upon completion of Cycle 2, subjects may use the investigative site's laboratory or their local laboratory for clinical laboratory assessments. Accredited certification, such as College of American Pathologists (CAP) and Clinical Laboratory Improvement Amendments (CLIA), and valid reference ranges must be collected for all clinical laboratories used by subjects.

The following clinical laboratory tests will be collected: Hematology, Coagulation, Blood Chemistry and PK Assessments.

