Serum chemistry ^{f, g}	X	X	Xf	Xf	X		X	X		X		X	
Coagulation	X												
Urinalysis ^h	X	Xc						X		X		X	
Pregnancy testing ⁱ	X	Xi						X		X		X	
PET/CT or CT (or MRI) scans (based on	X ^j								Xk		X ^k	X ¹	
indication) for response assessment													
CLL baseline assessments ^m	X												
PK/PD plasma sampling ⁿ		X			X	X	X						
Bone marrow aspirate/biopsy	Xº								X ^p		Xp		
Biomarker – tumor tissue ^q	X												
Biomarker – plasma tumor DNA ^r		X					X					X	
Biomarker – plasma cytokines ^s		X			X	X	X					X	
Biomarker – PBMC/B cell ^t	X												
Biomarker – saliva ^u	X												
LAM-002A administration in clinic ^v		X X X X											
Adverse events		Throughout Study											
Concomitant medications ^w							7	Γhroughou	ıt Study				
Long-term follow-up (F/U) ^x													X

Protocol: LAM-002A-NHL-CLN01

- A Eligibility will be confirmed by C1D1.
- B Complete physical examination (PE) will be performed at screening. A directed PE, including weight, will be performed within 72 hours prior to the start of each cycle and EOT.
- C Assessment/test does not need to be repeated on C1D1 if baseline was within normal limits and conducted within 72 hours of first dose.
- D Obtained on Day 1 for all cycles. For C1D1 and C1D10 obtained prior to dosing and 1 hour (± 15 minutes after dosing), 2 hours (± 30 minutes), 4 hours (± 1 hour), and 8 hours (± 1 hour) postdose. For C1D8 and C1D15, obtained prior to dosing.
- E Hematology includes hemoglobin, hematocrit, RBC count, platelet count, WBC and differential.
- F All hematology and chemistry laboratory parameters should be assessed at Screening and C1D1, C1D8, C1D15, C≥2D1 (all subsequent cycles), and then at least once prior to the start of all subsequent cycles and at EOT. Obtaining a chemistry laboratory parameter on Days 2 and Day 3 of Cycle 1 is only required in subjects with intermediate or high risk of TLS (per the risk definition in Section 6.8.1). Except for Days 1, 2, and 3 of Cycle 1, these parameters may be obtained within 72 hours prior to the planned day of collection. Abnormal test values should be monitored per protocol guidance.
- G Chemistry includes albumin, alkaline phosphatase, total bilirubin, BUN, calcium, carbon dioxide, chloride, creatinine, glucose, inorganic phosphorus, potassium, total protein, LDH, ALT, AST, sodium, and uric acid.

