- M Subjects with CLL/SLL must provide either a fresh blood sample containing circulating tumor cells or a bone marrow aspirate sample pretreatment. Tissue will be submitted for evaluation of the percentage of tumor cells and analysis of genetic alterations and/or gene expression that may predict anticancer activity and/or pharmacodynamic activity. In addition, for subjects with CLL/SLL, the sponsor may arrange for a portion of the sample to be evaluated at a sponsor-specified laboratory for known prognostic markers (e.g., quantitative immunoglobulins, FISH panel [chromosome 11q deletion, 13q deletion, 17p deletion and 12 trisomy], DNA mutational analysis for p53, IgHV [including IgHV3-21], and other genes of interest in CLL [e.g., Notch]; flow cytometry [for CD5, CD10, CD11c, CD19, CD20, CD23, CD38, CD45, kappa and lambda light chains and ZAP-70], and/or β2-microglobulin). The baseline bone marrow aspiration procedure (if required) should be performed after the study candidate has undergone the baseline radiology examination and is otherwise considered eligible for study participation. All subjects with CLL/SLL must have baseline imaging (with CT scans [preferred] or MRI scans).
- N Blood sampling for determination of the plasma concentrations and activity of LAM-002A and metabolites will be performed on C1D1 and C1D10 as follows: pre-dose, 30 minutes, 1, 2, 4, 6, 8 hours post-first dose of the day. Sampling on C1D8 and C1D15 will be pre-dose only. Subjects are required to come to the study site in a fasting state prior to the collection of certain PK samples.

Protocol: LAM-002A-NHL-CLN01

Version 9, 18 Feb 2020

- O Bone marrow aspirates/biopsies performed within 2 months prior to first dose may be used for clinical baseline assessments. For subjects with NHL, baseline bone marrow biopsies/aspirates may be omitted if not deemed essential for response assessment or patient management and there is another source of tumor tissue for pretreatment evaluation of gene expression and prognosis. For subjects with CLL/SLL, a baseline bone marrow aspirate is required unless the presence of sufficient circulating cells in the peripheral blood (e.g., absolute lymphocyte count [ALC] $\geq 10 \times 10^9$ /L) permits assessment of baseline parameters as described in Footnote m, above.
- P If necessary per applicable response criteria, a repeat bone marrow biopsy or aspirate will be required for subjects who have a CR by imaging and physical examination.

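### On the intermittent regimen, scheduled Cycle 1 safety laboratories (except Day 2–3 chemistry in subjects at TLS risk) fall 1.5 to 4.5 days after the last dose, and the Day 8 and Day 15 trough is not an on-treatment trough

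*Combined protocol and SAP*

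**What the plan says.** **Dosing.** Section 6.8.2.3 defines the intermittent regimen as "repeated 7-day sequences comprising BID self-administration for 3 days (6 doses) followed by 4 days without dosing". Section 6.8.2.6.2 refers to "each of the four 3-day courses of LAM-002A therapy during each 28-day cycle", and the evaluability rule in Section 6.6 uses "18/24 intermittent schedule".

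**Laboratories.** Table 9 footnote F reads "All hematology and chemistry laboratory parameters should be assessed at Screening and C1D1, C1D8, C1D15, C≥2D1 (all subsequent cycles". The same footnote then requires chemistry on Days 2 and 3 of Cycle 1, but only in subjects at intermediate or high TLS risk, and lets all other samples be drawn up to 72 hours early. Section 8.3.1 states "Samples will be collected from subjects at scheduled study visits before the administration of study drug unless otherwise noted", and permits extra samples when there is a clinical reason. The haematology and chemistry rows of Table 9 are empty on Day 10. That day is nevertheless a clinic visit on drug, with a full PK profile (footnote N), serial ECGs and vital signs (footnote D) and cytokines (footnote S).

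**PK.** Section 12 lists "trough concentrations on Days 8 and 15" among the parameters, without a separate rule for the intermittent regimen. For that regimen Table 9 footnote N says "Sampling on C1D8 and C1D15 will be pre-dose only" and places the full profile on Day 10. Table 13 footnote c assigns samples 8 to 14 to Day 10 for this regimen, so Table 13 contains no Day 8 sample for it.

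**The concern.** The primary endpoint is the frequency of DLTs in Cycle 1, and Section 6.1.1 evaluates both continuous and intermittent dosing. Several Table 4 criteria are laboratory values with no minimum duration: creatinine above 3.0 x ULN, bilirubin of Grade 3 or more, the combined bilirubin and transaminase criterion, and Grade 4 thrombocytopenia. An abnormality that appears during a three-day course and recovers in the days off could meet one of these criteria and not be present at the next scheduled sample. On continuous dosing the same visit days find the subject on drug, so the chance of detection differs between the regimens.

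The laboratory days match those of the continuous schedule, while PK, ECG, vital signs and cytokines were adapted to Day 10. That pattern is consistent with carry-over, though the documents give no reason for it. The PK wording has the same feature: one parameter label covers samples taken at very different times after a dose.

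**Working it through.** **Plan's own figure.** Four courses x 3 days x 2 doses = 24 planned doses, and 18/24 = 75%. This reproduces the evaluability threshold in Section 6.6 and fixes the dosing days as 1–3, 8–10, 15–17 and 22–24.

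**Assumption.** Doses are at 08:00 and 20:00, the example times in Section 6.8.2.3. Samples are at 08:00 before the dose, and no doses are missed.

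**Hours since last dose, intermittent regimen.**
- Day 8: from Day 3 20:00 to Day 8 08:00 = 5 x 24 − 12 = 108 h, or 4.5 days.
- Day 15: from Day 10 20:00, 108 h.
- Cycle 2 Day 1 (Day 29): from Day 24 20:00, 108 h.
- With the 72-hour laboratory window: 108 − 72 = 36 h, or 1.5 days. The earliest samples fall on Days 5, 12 and 26, all outside the dosing days.
- Days 2 and 3 (chemistry, TLS risk only): 12 h, on drug.
- Day 10 pre-dose: from Day 9 20:00 to Day 10 08:00 = 12 h, on drug.

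The laboratory range is therefore 36 to 108 h. From the Day 15 visit to Day 29 is nominally 14 days with no scheduled laboratory sample, and two courses (Days 15–17 and 22–24) are given in that time.

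**Continuous BID regimen.** A Day 8, 15 or 29 pre-dose sample is 12 h after the last dose. A sample drawn early within the window is still on drug.

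**PK samples.** Table 13 requires pre-dose draws within 30 minutes of dosing, so the 72-hour window does not apply. The intermittent Day 8 and Day 15 values are about 108 h post-dose, against 12 h for a continuous BID trough: 108/12 = 9 times as long. Section 4.1.4.1 gives a Day 14 terminal half-life of 12 to 21 h, so 108 h is 108/21 = 5.1 to 108/12 = 9.0 half-lives, after a faster early clearance phase.

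**Subjects concerned.** Section 6.2 lists Dose Levels 5–8 as open: 4 x 6 = 24. The 6 further subjects at the MTD or recommended dose bring the total to 30, but need not be on the intermittent regimen. The allowance is about 45.

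**The case against.** The strongest reply is that detection does not depend on these visits alone. Day 2–3 chemistry is on drug in subjects at TLS risk, and Section 6.8.1 makes one criterion sufficient for that status: raised LDH, a large node or a high lymphocyte count. In those subjects 2 of 5 post-baseline chemistry samples (Days 2, 3, 8, 15, 29) are on drug. Unscheduled samples are allowed. Grade 4 neutropenia must last at least 7 days to count, and asymptomatic Grade 3 chemistry elevations of 7 days or less that are not clinically relevant are excepted. Section 4.1.4.3 reports few laboratory signals so far. All of this stands and limits the point. It does not remove it: Day 2–3 chemistry covers only the first course, unscheduled sampling may not be prompted by a silent abnormality, and the exception sits in the Table 4 row for events not listed elsewhere, so it does not reach the renal and hepatic rows.

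Four stronger inferences are tempting but unsupported.
- A reader might infer that laboratory DLTs are sought only off drug, or that the intermittent MTD will be biased upward. The exceptions above rule out the first. The second needs onset and recovery times that the documents do not give.
- A reader might cite the Grade 3 hyponatraemia case. Section 4.1.4.3 attributes it partly to hydrochlorothiazide, and Table 4 might except it even if it were sampled on drug.
- A reader might take the Section 8.3 heading, "Screening/Baseline, Day 1, 8, 10, 15 (Cycles 1 and 2 Only) and Prior to Each Subsequent Cycle and End of Treatment", as already requiring Day 10 laboratories. That section also covers PK, and its haematology and chemistry subsections defer to the schedule tables.
- A reader might convert 108 h into a percentage of drug remaining. The terminal half-life applies only to what is left after the early phase, so such figures would be wrong.

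On PK, it can be said that the Day 8 value is the trough of a weekly period, that Section 12 already uses Day 10 for accumulation, and that Section 14.2 lets the SAP modify the plan. The correction is indeed one of labelling, but the protocol text as it stands gives one name to two quantities.

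**Conclusion.** The point holds in a limited form and merits an amendment. Apart from Day 2–3 chemistry in subjects at intermediate or high TLS risk and any unscheduled samples, scheduled post-baseline laboratories informing Cycle 1 on the intermittent regimen fall 1.5 to 4.5 days after the last dose. The matching continuous visits are on drug. The consequence is a lower chance of detecting brief laboratory DLTs that have no duration rule. Its size cannot be computed, because the documents give neither the kinetics of such events nor the proportion of subjects at TLS risk.

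The Day 8 and Day 15 intermittent trough of Section 12 is a washout value about 108 h post-dose, and Table 13 footnote c and Table 9 footnote N disagree on whether a Day 8 sample exists. These conclusions rest on the protocol's example dose times and on full adherence; end-of-treatment samples are not counted.

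**What to change.** 1. In Table 9 and footnote F, add haematology and serum chemistry at the existing C1D10 visit, drawn with the pre-dose PK sample. The cost is two tubes and a local laboratory run at a visit that already has seven PK draws. This covers the second course only; Days 15–17 and 22–24 would still have no on-drug sample, and the study report should say so. If the intermittent cohorts have already been treated, report the sampling times as a limitation instead.
2. In Section 12, define the on-treatment trough for the intermittent regimen as the C1D10 pre-dose concentration, and report the Day 8 and Day 15 pre-dose values as residual (washout) concentrations. The Day 10 sample is already planned, so this changes wording only.
3. Reconcile Table 13 footnote c with Table 9 footnote N on the Day 8 pre-dose sample, and clarify which assessments the Day 10 entry in the Section 8.3 heading refers to. This is also wording only.

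None of these changes alters a dose, a dosing schedule or a DLT criterion.
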